#### Expected participation in Phase 2 trial

We base proposed estimates on our experience conducting previous successful trials with Veterans with chronic pain (ACTION, SPACE, EPOCH, ECLIPSE). Study participants will be recruited from the Minneapolis, Indianapolis, Greater Los Angeles and Durham VA Health Care Systems, using a process successfully used in prior studies by members of our research team, and piloted during Phase 1 of this project. The four facilities have about 80,000 patients who meet our initial eligibility criteria. We estimate from our Phase 1 pilot a randomization rate of 2.5% but an increased randomization rate when using approach #2, email recruitment. Therefore, we will need to screen approximately 100,000 patients in order to reach our recruitment goal of up to 950 randomized. We want an approximately balanced sample of men and women. We estimate women will respond at up to 3 times the rate of men (approximately 4.5% for women and almost 2% for men). If we screen a large portion of the sample of eligible women (about 20,000) and about 1/3 of the eligible men (about 80,000), then we should reach our recruitment goal of up to 950 randomized, with nearly balanced men and women. Among those randomized, we are conservatively planning that up to 20% might be missing complete follow-up data but based on past work we believe the actual level of missing data will be closer

to 10-15%. Ultimately, this would yield a randomized N= up to 950 and with retention of 600 or greater participants at 6 and 12 months.

#### Power and Sample Size Estimate

Our power calculation uses the total BPI score as the primary outcome measure. For our primary analysis we estimate there will be 200 participants in each of the three treatment arms with complete data for a total of 600 people with complete data from a total of up to 950 randomized. Two hundred participants in each arm would yield 80% power to reject the null hypothesis of equal means if any of the three arms differed from each other by an effect size of 0.33 or greater. This is based on an alpha level of 0.0167 (Bonferroni correction of 0.05/3 = 0.0167) for each of the three comparisons (Mobile+Group vs Usual Care, Mobile vs Usual Care, and Mobile+Group vs Mobile). Using the same assumptions, there would be 90% power to detect differences of 0.38 or greater. The BPI has been found to have a minimally clinically important difference of approximately 1 point and the standard deviation from prior studies is around 2 points, which is consistent with a minimally important clinical difference in effect size of around 0.5.

As a secondary analysis we will look at a categorical responder analysis, in which we define clinically significant changes as a 30% reduction in BPI score from baseline. This is an accepted threshold for clinically significant improvement in clinical trials and recommended by the IMMPACT guidelines.

Previous studies demonstrate that a 30% reduction on the BPI is a clinically important difference. Prior studies have shown that 15-20% of UC patients demonstrate a 30% reduction in pain function score from baseline to follow-up. With 200 people in each arm there would be 80% power to detect absolute differences of greater than 13.3%, 14.3%, and 16%, respectively, based on assumptions of 15%, 20% or 35% in the comparison arms (accounting Bonferroni corrections for comparisons of Mobile+Group vs Usual Care, Mobile vs Usual Care, and Mobile+Group vs Mobile).

Based on the conservative estimate of 20% attrition, we propose randomizing at least 250 per arm to ensure that we maintain a minimum effective size of 200 per group (250 people per group\*.80=200). If we instead achieve the anticipated attrition rate of only 10% then our sample will be approximately 225 per arm.

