Due to COVID-19, VA ORD has placed an administrative hold on research activities involving non-critical, in-person contacts between study participants and VA research staff. However, VA ORD permits group meetings via platforms that are approved by the ISSO. Following these guidelines, we plan to move the Mobile+Group MBI to an online format which will be delivered weekly, per the study protocol, using University of Minnesota (UMN) Zoom, a VA and HIPAA compliant videoconferencing software. Participants will be required to log into Zoom with a unique code. We will not be video or audio recording the Zoom sessions or collecting PHI or other sensitive participant info. This Zoom technology is on the VA Technical Reference Model (TRM), a list of VA-approved technologies. The UMN Zoom platform is currently being used by Co-Investigators [name] and [name] (NIH #1R21AT009110-01A1), to deliver a Group MBI remotely, due to COVID-19.

The Mobile MBI consists of the same training modules delivered on an app (and available online), with no group interaction but with up to 3 one-on-one phone calls with a facilitator. Inclusion of this condition will allow us to rigorously test the addition of the group component of the MBI. This is important because, although the group experience is considered to be a key part of MBIs and there is some evidence that it increases engagement, there is little research designed to rigorously test the added benefit of groups, relative to its costs. Specifically, the Mobile MBI requires fewer VHA resources (e.g., use of trained facilitators), reduces access barriers associated with scheduling synchronous sessions and reduces barriers associated with the group format. However, the Mobile+Group MBI affords benefits related to having a facilitator and a group (e.g., accountability, support, motivation, feeling of common humanity and shared struggle), which may increase participation, engagement and lead to improved outcomes.

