#### Primary hypotheses:

- 1. Mobile MBIs will be more effective at improving chronic pain (as measured by change in BPI over the 12-month follow-up period) compared to usual practice
- 2. Mobile+Group MBIs will be more effective at improving chronic pain (as measured by change in BPI over the 12-month follow-up period) compared to usual practice
- 3. Mobile+Group MBIs will be more effective at improving chronic pain, as measured by BPI change over the 12-month follow-up period, compared to Mobile MBIs without the group component.

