#### General Analytic Approach.

We will use an intention-to-treat approach. Preliminary descriptive analyses will summarize the distributions of the baseline measures across treatment arms overall and by gender and will similarly assess the outcome distributions across assessment time points. We will summarize the completeness of the self-reported outcome assessments and examine associations between completeness and baseline measures as well as the association with secondary outcome assessments that are collected from the electronic medical record (e.g. medications, health care utilization related to pain treatment). In previous studies, we have observed outcome completion rates in excess of 90% at each assessment time-point. Initial analyses will use all

available follow-up data and subsequent sensitivity analyses will examine the potential effect of response bias.

For analyses of the primary outcome, all repeated measurements of the BPI score will be fitted in a mixed model for repeated measures as a function of the group assignment, while controlling for time points and baseline values of the outcome as fixed effects, with participants as random effects. Between-group differences over the entire follow-up period will be tested as the primary test of treatment group differences (this will be done for all three comparisons of the Mobile, Mobile+Group, and Usual Care arms). Between-group differences will be estimated for each of the time points (e.g. 10 weeks, 6 months and 12 months). The secondary outcomes physical function, anxiety, depression, fatigue, sleep disturbance, participation in social roles and activities, patient-ratings of improvement, and PTSD) will be similarly analyzed using the same linear mixed effect models for normal continuous measures and appropriate generalized linear mixed effect models for non-normal measures. For example, the BPI responder analyses will use generalized linear mixed effect models with binomial distributions and either log or logit links, which ever best fit the data, for the repeated dichotomous outcomes of a 30% reduction from baseline in BPI scores over the 12-month study period.

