## 6.0 Reporting

We will follow the VA Central IRB reporting requirements for all issues that must be reported (i.e. unanticipated serious adverse events (U-SAEs), unanticipated problems (UAPs), protocol deviations/violations/noncompliance, and any changes with respect to the protocol). The study staff will remain in regular contact (by phone, email, and face-to-face) to discuss study processes, progress, and any issues encountered. Any issues will be reported directly to the PI. Data will be reviewed regularly to ensure accuracy and data privacy. In the case of problems, the project coordinator will immediately discuss with the study PI. The PI in turn will report any problems to the Central IRB accordingly (e.g., completing forms 119 or 129) within 5 business days of learning of the problem(s). If there are modifications or amendments to the study the study PI will also complete the appropriate Central IRB form (i.e., 116) and wait for approval prior to implementation. Additionally, all unanticipated deaths that are related to a research study overseen by the VA Central IRB must immediately be reported orally to the VA Central IRB wia the toll-free number [contact].

The current application is for a low-risk clinical trial. The Study Coordinator and participants are not blinded to the study condition group assignment. Therefore, we believe, [name], as the PI, can be responsible for carrying out the Data Safety Monitoring Plan (DSMP) throughout the entire study period. [name] will thus be responsible for overseeing and ensuring an IRB-compliant process for reporting Adverse Events (AEs), including Serious Adverse Events (SAEs), and Unanticipated Problems (UPs), should any occur.

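### Optional gain: a step-down rule for the three primary comparisons keeps every rejection at 0.0167 and adds power within the same 5% familywise error

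*Combined protocol and SAP*

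**What the plan says.** Section 5.6, Power and Sample Size Estimate, sets the level: "This is based on an alpha level of 0.0167 (Bonferroni correction of 0.05/3 = 0.0167) for each of the three comparisons". With 200 completers per arm, it claims 80% power to "reject the null hypothesis of equal means if any of the three arms differed from each other" by 0.33 SD, and 90% power at 0.38 SD. It puts the BPI standard deviation at about 2 points and the minimally important difference at about 1 point, "which is consistent with a minimally important clinical difference in effect size of around 0.5". It plans for 20% attrition (250 randomized per arm) and adds: "If we instead achieve the anticipated attrition rate of only 10% then our sample will be approximately 225 per arm".

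Section 5.6, General Analytic Approach, makes the between-group difference over the whole follow-up the primary test and says "this will be done for all three comparisons of the Mobile, Mobile+Group, and Usual Care arms". It gives no test level there, and the documents contain no step-down or closed testing rule.

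The hypotheses in 3.0 and 5.1 are worded directionally, for example "Mobile+Group MBIs will be more effective at improving chronic pain, as measured by BPI change over the 12-month follow-up period".

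**The concern.** Bonferroni protects against all three nulls being true together. With three means, that can happen only if all the means are equal. Once one pairwise equality is false, at most one of the other two can hold, so dividing alpha by three for the remaining tests is stricter than 5% familywise control requires.

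Under the flat rule, a primary contrast with p between 0.0167 and 0.05 counts as negative even when another contrast has already been rejected. That could decide whether both interventions are shown to differ from usual care. It could also decide whether the group component is shown to add anything over the cheaper arm, a comparison the Introduction motivates on resource grounds: "Specifically, the Mobile MBI requires fewer VHA resources". The documents do not rank the three effects, so any of the contrasts could be the one affected.

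**Working it through.** **Inputs from section 5.6.** Three contrasts; alpha 0.05/3 = 0.0167 each; 200 completers per arm; design effects 0.33 and 0.38 SD; SD about 2 BPI points; 225 per arm at 10% attrition. Also 253 per arm, from 950 × 0.80 / 3. The effects of 0.25 and 0.40 SD below are assumptions for illustration and are not in the documents.

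**1. The plan's own figure.** The noncentrality is d × √(n/2) = 0.33 × √100 = 3.3. The two-sided t test at 0.0167, with pooled SD and 3 × 199 = 597 df, gives 81.5%. At 0.38 SD it gives 91.9%, and at 0.50 SD 99.5%. These agree with the stated 80% and 90%. A one-sided test at 0.0167 would give about 88% and 95%, so the plan's figures fit two-sided tests of equality.

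**2. The step-down rule.** Test the smallest p-value at 0.05/3. If it is rejected, test each of the other two at 0.05; otherwise stop.

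**3. Familywise error.**
- All three means equal: an error requires the smallest p to be at or below 0.0167, so its probability is at most 3 × 0.0167 = 0.05.
- Exactly one equality true: that contrast is never tested above 0.05, so the error is at most 0.05.
- Exactly two equalities true: impossible, because two imply the third.

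Any p at or below 0.0167 is still rejected, so nothing is lost.

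**4. Power.** Simulation with 400,000 trials per scenario, normal outcomes, pooled SD and two-sided t tests; the simulation standard error is at most 0.08 percentage points. Effects are in SD units against usual care (UC).

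| Per arm | Mobile, Mobile+Group | What is shown | Flat 0.0167 | Step-down |
|---|---|---|---|---|
| 200 | 0.33, 0.33 | each vs UC | 82% | 88% |
| 200 | 0.33, 0.33 | both vs UC | 71% | 83% |
| 200 | 0.40, 0.40 | both vs UC | 90% | 96% |
| 200 | 0.50, 0.50 | both vs UC | 99.1% | 99.8% |
| 200 | 0.25, 0.50 | each 0.25 step | 54% | 70% |
| 200 | 0.25, 0.50 | all three | 21% | 44% |
| 200 | 0.33, 0.50 | Mobile+Group vs Mobile | 24% | 40% |
| 225 | 0.33, 0.33 | both vs UC | 78% | 88% |
| 225 | 0.25, 0.50 | each 0.25 step | 60% | 75% |
| 253 | 0.33, 0.33 | both vs UC | 84% | 92% |

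The chance of at least one rejection is the same under both rules (92.2% at 200 per arm with both effects 0.33). No flat-rule rejection was lost in any run.

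**5. Error rates in the simulation.** Familywise error was about 0.044 with all means equal and 0.049 to 0.050 with one true null. With both interventions at 0.33 SD and 200 per arm, the true-null contrast of Mobile+Group against Mobile was rejected 1.7% of the time under the flat rule and 5.0% under the step-down.

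**6. Size of the added findings.** An added rejection has an observed difference between t(0.05) × √(2/200) = 0.196 SD and t(0.0167) × √(2/200) = 0.240 SD. With an SD of 2, that is 0.39 to 0.48 BPI points. Its 98.33% interval always includes zero.

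**The case against.** The strongest reply is that the sponsor chose a valid correction and powered for it, so this is a matter of preference. It is indeed optional. The more specific objections are these.

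- **Clinical size.** Every added rejection at 200 per arm has an estimate below half of the plan's 1-point important difference. This stands as a limit on interpretation. But the flat rule does not screen for clinical importance either: it already rejects from about 0.48 points. The plan also powers the trial for 0.33 SD, where the gain is real.
- **More false positives on a single contrast.** The rise from 1.7% to 5.0% is a genuine cost, and it includes the contrast on the group component. Familywise error nevertheless stays within 5%.
- **Directional hypotheses.** With one-sided nulls the 0.05 step fails. If Mobile is better than usual care, Mobile+Group can still be no better than either. The rule therefore needs an explicit statement of two-sided equality nulls. Holm's procedure (0.0167, 0.025, 0.05) needs no such statement and keeps part of the gain: about 77% rather than 83% for showing both at 0.33 SD. It is a sound alternative with less power. Counting wrong-direction rejections as errors kept the total within 5% in the scenarios tried, which is not a general proof.
- **Clustering.** Mobile+Group participants meet in groups, while the model has random effects for participants only. Assuming groups of 10 and an intraclass correlation of 0.01 to 0.05 (neither is in the documents), a true-null contrast involving that arm would be rejected 5.5% to 7.7% of the time at 0.05, against 1.9% to 3.1% at 0.0167. That is a separate defect of the model, but the flat rule does hide more of it.
- **Timing.** The protocol is Version 16, dated March 2024. The documents do not show whether comparative data have been seen. The change is defensible only if they have not.

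**Conclusion.** The point holds as an optional improvement, not as a correction. At the plan's own design effect of 0.33 SD and 200 per arm, the step-down raises the chance of showing both interventions differ from usual care by 12 percentage points, at the same familywise error and without extra participants. The gain concerns second and third rejections only. It largely disappears if both effects reach 0.5 SD. It also does not rescue a small contrast: Mobile+Group against Mobile at a difference of 0.17 SD reaches only 40%.

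The conclusion rests on two-sided equality nulls, tests that hold their nominal level, independent observations and the stated completer numbers. Baseline adjustment and repeated measures are not credited; they would raise power under both rules.

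**What to change.** Add one paragraph to section 5.6, General Analytic Approach:

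- The three primary contrasts are two-sided tests of equality, with direction read from the sign of the estimate.
- The smallest p-value is tested at 0.05/3. If it is rejected, each of the other two is tested at 0.05; otherwise testing stops.
- The present power figures are kept as the conservative bound.
- Unadjusted 95% intervals, which agree with the added rejections, are reported beside 98.33% intervals. The latter are labelled as not matching the step-down decisions.

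The cost is the text, a second set of intervals and the two downsides above: up to 5% rejection of a true-null contrast after another rejection, and 98.33% intervals that include zero for every added rejection.

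The rule must be fixed before any look at comparative data, not merely before database lock, because "The Study Coordinator and participants are not blinded to the study condition group assignment". If that is no longer possible, or the sponsor prefers the simpler rule, flat Bonferroni remains valid; 0.0167 should then be stated as the analysis level in the same section.

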#### General Analytic Approach.

We will use an intention-to-treat approach. Preliminary descriptive analyses will summarize the distributions of the baseline measures across treatment arms overall and by gender and will similarly assess the outcome distributions across assessment time points. We will summarize the completeness of the self-reported outcome assessments and examine associations between completeness and baseline measures as well as the association with secondary outcome assessments that are collected from the electronic medical record (e.g. medications, health care utilization related to pain treatment). In previous studies, we have observed outcome completion rates in excess of 90% at each assessment time-point. Initial analyses will use all

available follow-up data and subsequent sensitivity analyses will examine the potential effect of response bias.

For analyses of the primary outcome, all repeated measurements of the BPI score will be fitted in a mixed model for repeated measures as a function of the group assignment, while controlling for time points and baseline values of the outcome as fixed effects, with participants as random effects. Between-group differences over the entire follow-up period will be tested as the primary test of treatment group differences (this will be done for all three comparisons of the Mobile, Mobile+Group, and Usual Care arms). Between-group differences will be estimated for each of the time points (e.g. 10 weeks, 6 months and 12 months). The secondary outcomes physical function, anxiety, depression, fatigue, sleep disturbance, participation in social roles and activities, patient-ratings of improvement, and PTSD) will be similarly analyzed using the same linear mixed effect models for normal continuous measures and appropriate generalized linear mixed effect models for non-normal measures. For example, the BPI responder analyses will use generalized linear mixed effect models with binomial distributions and either log or logit links, which ever best fit the data, for the repeated dichotomous outcomes of a 30% reduction from baseline in BPI scores over the 12-month study period.

Additional exploratory analyses involve the assessment of the extent to which amount of mindfulness practice, pain acceptance, pain-related fear avoidance, pain management self-efficacy, mindfulness skills, and perceived stress mediate the effects of the intervention. The indirect effects of these potential mediators will be tested using the bootstrap approach to obtaining confidence intervals to avoid the often-violated assumption underlying Sobel's (1982) method that the sampling distribution of the indirect effect will be normal. Similar to the methods described above for the primary analyses, weighted selection model analyses will examine sensitivity of results to response biases.

To assess the sensitivity of these initial analyses to response bias, we will fit a series of weighted selection model analyses. Each analysis will use an EM algorithm to estimate weights to assign to potential values of the missing outcomes for use in the regression model. Models will be varied to use different combinations of the following variables—intervention, observation and value of the outcome at various assessments, and baseline covariates together with pain measurements and services utilization over the follow-up period—as predictors to consider different potential missing at random and missing not at random mechanisms generating the missing data.

It has been hypothesized that men and women may respond differently to the interventions and this might be particularly true for the group-based portions of the intervention. An interaction between treatment and gender will be assessed, however tests for interaction tend to be underpowered and this is an important area of concern, so gender stratified results will be presented in secondary analyses even if statistical evidence of interaction is not found.

